2.2 Secondary Objectives

- To quantify the incidence of moderate to severe capsular contracture
- To quantify the rates of minor revisional surgeries
- To evaluate cosmesis
- To quantify post-radiation volumetric and capsular changes on MRI and correlate these changes with clinical assessments of capsular contracture.

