9.3 Assessment of Secondary Objectives

9.3.1 Capsular Contracture

Two methods will be employed to assess capsular contracture. These include the current standard assessment tool, the Modified Baker score, and MRI. All follow-up assessments will be compared to the baseline assessments. For all patients, the radiation oncologist should perform the baseline physical evaluation 3-10 weeks after the patient's exchange surgery.

Baker Scoring System (See Appendix 1)

All patients will be assigned a Baker Classification score at baseline and at each follow-up interval by the radiation oncologist and plastic surgeon. The Baker score is a standardized 4-point scale, which integrates the texture and appearance of the breast. Grade I is a normal-appearing, soft breast (a Grade IA breast cannot be detected as an implant, while the implant of a Grade IB breast can be detected by physical examination or inspection); Grade II refers to breast implants that are firm but

appear normal; Grade III includes implants that are firm and appear abnormal; Grade IV capsular contracture is the most severe and includes breasts that are hard, painful, and appear abnormal often with severe distortion [46].

Breast MRI

Longitudinal MR studies will be evaluated for capsular contracture.

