14.1.2 Capsular Contracture

For the secondary objectives, the incidence of moderate and severe capsular contracture will be examined using proportions of patients who developed Baker grade <II and \geq II capsular contracture, respectively, at 12 or 18 months and 24 or 30 months after IMRT was administered. Incidence of minor revisional surgeries by plastic surgeon will be evaluated by proportions too. Again, the rates (proportions) will be compared across the two groups.

To evaluate cosmesis, the Breast-Q[®] will be utilized in these assessments and will be presented descriptively, giving summary statistics for changes in the Breast-Q[®] scores over time.

Post-treatment MRI outcome is defined as a continuous variable. We will examine the correlation between the 12-month MRI and 12-month Baker score (<II vs \geq II in Group 1 and between the 18-month MRI and 18-month Baker's score in Group 2. The correlation will be assessed by Wilcoxon rank sum tests. We will also examine the sensitivity and specificity of MRI by using Baker score as the gold standard. All patients enrolled will be used for the analysis of secondary objectives if they provided eligible measurements. Analyses for secondary objectives will be done separately for the two groups.

14.1.3 $^{13}\text{N-NH}_3$ PET/CT Feasibility Endpoint

We will assess the feasibility of performing $^{13}\text{N-NH}_3$ PET studies in breast cancer patients undergoing IMRT within the RT simulation session. This involves delivering the dose on time (taking into account the short half life of $^{13}\text{N-NH}_3$), performing all scans successfully, and most importantly, having the patient tolerate all imaging sessions while in the treatment position.

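### The MRI–contracture correlation in 14.1.2 uses one follow-up MRI value and a two-level Baker score, so it does not answer the change objective in 2.2 and discards planned data

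*Combined protocol and SAP*

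**What the plan says.** The secondary objective in Section 2.2 is "To quantify post-radiation volumetric and capsular changes on MRI and correlate these changes with clinical assessments of capsular contracture". Section 9.3.1 adds that "All follow-up assessments will be compared to the baseline assessments", without giving a method.

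The analysis is in Section 14.1.2:

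- The MRI variable: "Post-treatment MRI outcome is defined as a continuous variable". No MRI parameter is named and no change score is defined.
- Group 1: "We will examine the correlation between the 12-month MRI and 12-month Baker score", with Baker split at <II vs ≥II.
- Group 2: the comparison is "between the 18-month MRI and 18-month Baker's score in Group 2". The two-level split is not repeated here.
- The test: "The correlation will be assessed by Wilcoxon rank sum tests".
- Sensitivity and specificity of MRI against Baker are also planned. No MRI cut-point or use of baseline is stated.
- The two groups are analysed separately.

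Section 12.0 plans to correlate post-treatment MRI with clinical assessment and says that the quantification of post-radiation change will be descriptive. Section 9.3.1 describes Baker as a 4-point scale. Sections 10.1 and 10.2 schedule optional MRI and clinical evaluation at 12 and 24 months (Group 1) and at 18 and 30 months (Group 2).

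**The concern.** The objective is about change, but the specified correlation uses the MRI value at a single visit. A patient's follow-up value carries whatever capsule and implant dimensions were present at baseline as well as any change since. A relation between that value and Baker grade is therefore not the relation named in the objective.

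A rank-sum test also compares two samples. It forces the Baker grade into two classes, treats grades II, III and IV as the same outcome, and on its own reports no size of association. The second follow-up pair, at 24 or 30 months, has no place in the correlation.

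MRI is optional (Section 4.2.3) and the groups are analysed separately, so the numbers may be small. The stated objective could go unanswered although most of the data for it are collected, and the test that is run would be weaker than it needs to be.

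**Working it through.** **1. Objective against analysis.** The documents give no alpha, power, effect size or number of MRI patients for this analysis, so there is no stated figure to reproduce.

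| Element | Objective or data planned | Correlation in 14.1.2 |
|---|---|---|
| MRI variable | Change after radiation (2.2) | Value at 12 or 18 months |
| Baseline MRI | Collected (4.2.3, 8.0); comparison promised (9.3.1) | Not used |
| Second follow-up | MRI and clinical evaluation at 24/30 months (10.1, 10.2) | Not used |
| Baker grade | Four ordered grades (9.3.1) | <II vs ≥II: explicit for Group 1, implied by the two-sample test for Group 2 |

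**2. What baseline means in each group.** Under Section 8.0, the Group 1 baseline MRI must be completed before IMRT starts. The Group 2 baseline MRI is about 6–8 months after IMRT. Section 11.2 bars MRI while an expander is in place, so Group 2 cannot have a pre-radiation scan on this plan. Change from baseline is a pre- to post-radiation change in Group 1 only. In Group 2, assumed in 14.1.1 to be two-thirds of patients, it is a post-exchange change.

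**3. Effect of the two choices on power.** Every input here is an assumption: n = 30 MRI patients in a group, two-sided 0.05, and Baker I/II/III/IV at 40/30/22/8%. Change is D ~ N(0, 1), baseline is B ~ N(0, s²) with s = 0.5 or 1, and follow-up is F = B + D. Baker comes from a latent variable L cut at its 40th, 70th and 92nd percentiles, with ε ~ N(0, 1):

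- Model A, change drives contracture: L = 0.5·D + √0.75·ε.
- Model B, absolute follow-up value drives contracture: L = 0.5·F/√(1 + s²) + √0.75·ε.

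In each model the MRI variable that is not the driver has its correlation with L reduced to 0.5/√(1 + s²). That is 0.5/√1.25 = 0.45 for s = 0.5 and 0.5/√2 = 0.35 for s = 1. The model chosen therefore decides which variable looks better.

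Simulated power:

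| Model | s | Follow-up MRI, two-level Baker, rank sum (planned) | Follow-up MRI, ordinal Baker, Spearman | Change, ordinal Baker, Spearman |
|---|---|---|---|---|
| A | 0.5 | 0.48 | 0.60 | 0.72 |
| A | 1 | 0.30 | 0.40 | 0.71 |
| B | 0.5 | 0.59 | 0.74 | 0.61 |
| B | 1 | 0.58 | 0.72 | 0.40 |

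With 2,000 replicates the Monte Carlo standard error is at most √(0.25/2000) = 0.011 per entry.

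*Ordinal against two-level, same MRI value.* The gains are 0.60 − 0.48 = 0.12, 0.40 − 0.30 = 0.10, 0.74 − 0.59 = 0.15 and 0.72 − 0.58 = 0.14. The gain appears in every row.

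*Change against follow-up value, both ordinal.* The differences are 0.72 − 0.60 = +0.12, 0.71 − 0.40 = +0.31, 0.61 − 0.74 = −0.13 and 0.40 − 0.72 = −0.32. The sign reverses with the model.

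**4. Sensitivity of the ordinal gain.** A second set of runs used n = 34 or 66 (the primary-cohort minima in 14.1.1, not MRI numbers), latent correlation 0.45 with change, baseline/follow-up MRI correlation 0.3, 0.5 or 0.8, and 25–60% of patients in grade I. For the follow-up MRI, ordinal Baker did at least as well as two-level in all 18 settings. The gain ran from nil (0.10 against 0.10) to 0.16 (0.33 to 0.49), and was small where baseline and follow-up MRI were highly correlated and neither test had much power.

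**The case against.** The strongest reply is that the plan separates two tasks on purpose. Section 12.0 correlates post-treatment MRI with clinical findings and leaves the quantification of change descriptive; 14.1.2 follows that split. Section 9.3.1 promises a baseline comparison, and sensitivity and specificity are planned as well. This stands to the extent that baseline is missing from the specified correlation and not from the whole protocol. It does not close the gap, because Section 2.2 promises to correlate change as well as to quantify it, and no section gives a method for that.

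Second, the motivating study described in Section 3.0 was cross-sectional and compared absolute capsular thickness between two Baker classes, and the same section notes that Baker grading is subjective. Collapsing grades is therefore permissible, and the rank-sum test is a valid test of association between a continuous and a two-level variable. Both points stand, and they support keeping that comparison as a supplement. That study grouped I with II, however, so it does not support the <II vs ≥II split used here, and it had no baseline scan to use.

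Third, a reader might infer that leaving out change costs the plan a large amount of power, for example 0.72 against 0.48 or 0.30. The documents do not support that. The comparison changes two things at once and assumes that change drives contracture. If the absolute value drives it, as the cross-sectional study would allow, the planned test has power 0.58 against 0.40 for change with ordinal Baker (n = 30, s = 1).

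Fourth, making change the MRI variable in both groups would not deliver the objective in Group 2, where the baseline scan follows IMRT. This stands in full.

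**Conclusion.** The point holds as a mismatch between objective and analysis, together with an avoidable loss of information. The correlation in 14.1.2 omits the baseline MRI, the 24/30-month pairs and the ordering of Baker II to IV.

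The size that can be defended is the gain from ordinal Baker: 0.10 to 0.15 in power at n = 30, from 0.30–0.59 to 0.40–0.74, under either model. It rests on an assumed correlation of 0.5, the assumed Baker mix and the assumed number of MRI patients. It can be close to nil where neither analysis has power.

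The case for adding change rests on the wording of Section 2.2 and not on power. It would be wrong to conclude that the follow-up value is the inferior variable, or that baseline is ignored throughout the protocol. This concerns a secondary objective and does not touch the primary analysis. The plan should be amended.

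**What to change.** Amend 14.1.2 as follows, naming the MRI measure or measures to be used.

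1. In both groups, correlate the follow-up MRI value with the ordinal Baker grade by Spearman or Kendall's tau with a 95% CI, at 12/18 months and at 24/30 months. Keep the two-level rank-sum comparison as a supplement. Section 14.1.3 already proposes rank correlation for the PET data.
2. In Group 1, where the baseline MRI precedes IMRT, add the correlation of change from baseline MRI with Baker grade. Report it beside the follow-up-value result, which includes all patients with a follow-up MRI.
3. In Group 2, keep the follow-up value as the main MRI variable. Label any change from baseline as a post-exchange change, and state that a pre- to post-radiation change cannot be estimated in this group.

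The cost is SAP wording and a little more analysis, since all the data are already planned. Patients without a baseline MRI do not enter the change analysis, so the number contributing to each result should be reported.

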2.0 OBJECTIVES AND SCIENTIFIC AIMS

2.1 Primary Objective

To evaluate the efficacy of multi-beam IMRT in decreasing the rate of implant failure in breast cancer patients who have undergone two-stage expander/implant reconstruction and require PMRT. Implant failure is defined as a surgery requiring removal or replacement of the prosthesis with another type of reconstruction.

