MSKCC's institutional experience of 151 patients who received PMRT following expander/implant reconstruction, the 7-year permanent implant failure rate was 29%, with the majority of events occurring within 1-2 years after radiation. Infection was a major cause of implant removal, whereas capsular contracture was the most dominant cause for implant replacement. This data is consistent with multiple reports in the literature where capsular contracture remains the most significant long-term risk following irradiation of implant reconstructions, even with improvements in implant technology and surgical techniques over the past decade [13-16]. Recently, additional data from MSKCC has been published by Cordeiro et al [51], which demonstrated that implant failure rate was higher when patients were irradiated to the tissue expander vs. the permanent implant, thereby demonstrating the significance of the timing of radiation therapy relative to reconstruction when assessing reconstructive outcomes.

Existing Methods for Assessing Capsular Contracture and Cosmesis After Implant Reconstruction

To date, the standard tool for estimating the presence and severity of capsular contracture is the Baker scale, which was developed in 1979 and consists of a standardized 4-point scale that integrates the appearance, texture and tenderness of the examined breast. Studies have shown that the Baker score can be subjective and lead to inter-rater (and possible intra-rater) variability [5].

Methods such as measurement of pressures inside the breast pocket using tonometry or other techniques have been attempted. However, none of these tools have gained widespread acceptance. Subsequently, there is difficulty in assessing the extent of capsular contracture, resulting in a wide range of capsular contracture rates reported in the literature [17]. The lack of an objective way to measure capsular contracture has hindered efforts to establish standardized treatment guidelines for capsular contracture.

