8.0 PRE-TREATMENT EVALUATION

Groups 1 and 2, will have a baseline clinical evaluation 3-10 weeks after permanent implant exchange, both by the radiation oncologist and by the plastic surgeon. For Group 1, baseline evaluations will take place shortly before or during IMRT (but the baseline MRI must be completed prior to the start of IMRT). For Group 2, MRI and baseline evaluations will take place approximately 6-8 months after completion of IMRT. The baseline procedures include:

- History and physical exam by a radiation oncologist and a plastic surgeon, including clinical evaluation for implant failure, revisional surgeries, capsular contracture and cosmesis
- Breast-Q® questionnaire
- MRI of the breast (strongly recommended, but not required)
- CBC (Complete Blood Count)
- FACT-B and FACIT questionnaires (only Groups 2A and 2B)

However, at the discretion of the plastic surgeon, the baseline clinical evaluation by plastic surgeon may occur at any time point between the exchange surgery and 10 weeks post-surgery.

The research team will collect baseline demographic data that may relate to possible variability in the study population. Data to be collected includes details on chemotherapy, hormone therapy and surgery.

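### Section 14.1.2 answers an incidence objective with a contracture rate that depends on the patient still having a prosthesis to grade

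*Combined protocol and SAP*

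**What the plan says.** The objective in section 2.2 is an incidence: "To quantify the incidence of moderate to severe capsular contracture".

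Section 14.1.2 estimates it with simple proportions of patients who developed Baker grades below II, and II or above, at 12 or 18 months and at 24 or 30 months after IMRT. The population rule is "All patients enrolled will be used for the analysis of secondary objectives if they provided eligible measurements". What makes a measurement eligible is not stated.

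Under section 9.3.1 each patient is "assigned a Baker Classification score at baseline and at each follow-up interval". The form schedule in section 16.1 matches: the grading forms fall 3–10 weeks after exchange surgery and at follow-up.

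The primary endpoint can occur at any time from the end of IMRT to the end of follow-up (sections 1.0 and 12.0). Section 2.1 defines it: "Implant failure is defined as a surgery requiring removal or replacement of the prosthesis with another type of reconstruction".

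On the institution's earlier series, section 3.0 says of failures, "with the majority of events occurring within 1-2 years after radiation", and of their causes, "Infection was a major cause of implant removal, whereas capsular contracture was the most dominant cause for implant replacement".

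**The concern.** The event that ends grading is the primary endpoint, and the protocol names contracture as one of its main causes. A patient who loses the prosthesis before a visit has no capsule to grade there. Nothing in the plan counts a contracture-related loss as a contracture event, carries the last grade forward, asks for a grade at explant, or treats loss as a competing event. The proportion is then computed in a group selected partly by the outcome it measures.

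The scheduled grades close the gap only in part. In Group 1 the baseline falls shortly before or during IMRT (section 8.0), so the first later grade is at 12 months. Group 2 has an earlier one: "For Group 2, MRI and baseline evaluations will take place approximately 6-8 months after completion of IMRT". That grade follows the exchange, so a Group 2 patient who loses the expander before exchange is never graded.

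At stake is the meaning of the first-listed secondary result. A reader would take it as the risk of contracture after IMRT, when it is the prevalence or risk among those who kept the prosthesis.

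**Working it through.** **The plan's own figures.** The plan states no contracture rate, sample size or precision, so there is none to reproduce. The only figures to borrow are the failure rates in section 14.1.1: 20% (Group 1) and 30% (Group 2) historically, with 26% unacceptable and 16% acceptable for the pooled cohort. The one-third/two-thirds mix gives (20 + 2 × 30)/3 = 26.7%, which the plan writes as 26%. The difference does not matter here.

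**Formula.** Let f be the share who lose the prosthesis ungraded, c the rate among graded patients (what section 14.1.2 would report) and s the share of the ungraded losses attributable to contracture.

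- All-patient rate = (1 − f)c + f·s
- Error of the reported rate = (1 − f)c + f·s − c = f(s − c)
- The reported rate is too low if s > c, too high if s < c, and correct if s = c.

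**Size of f.** If every failure by the final visit were ungraded, f would be 16–26%. This is an upper bound. If *developed* is read cumulatively, a patient with a qualifying grade before the loss still counts. At the first visit f is smaller and not given. If 25% of losses precede that visit (assumption), f = 0.25 × 16% to 0.25 × 26% = 4–6.5%. If 75% do, f = 12–19.5%.

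**Bounds with no assumption about s.** Setting s to 0 and to 1 gives (1 − f)c to (1 − f)c + f, a width of f. With c = 25% as an illustration:

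| f | Lower | Upper |
|---|---|---|
| 16% | 0.84 × 25 = 21.0% | 37.0% |
| 26% | 0.74 × 25 = 18.5% | 44.5% |
| 20% (Group 1, historical) | 0.80 × 25 = 20.0% | 40.0% |
| 30% (Group 2, historical) | 0.70 × 25 = 17.5% | 47.5% |

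**Sign under assumed values.** Take f = 26% and let s range over 30–70% (assumption).

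- Grade III/IV, c assumed 15–35%: from 0.26 × (0.30 − 0.35) = −1.3 points to 0.26 × (0.70 − 0.15) = +14.3 points.
- Grade II or above, c assumed 40–60%: from 0.26 × (0.30 − 0.60) = −7.8 points to 0.26 × (0.70 − 0.40) = +7.8 points.

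Positive means the reported rate is too low. Both signs occur in both cases.

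**Between groups.** Section 14.1.2 also says the rates will be compared across groups. With the same s and c in both groups, the distortion is (0.30 − 0.20)(s − c). That is −0.5 to +5.5 points for the III/IV values above, and −3.0 to +3.0 for II or above. With 34 and 66 patients (the primary-cohort minimums) and a 25% rate, the standard error of the difference is √[0.25 × 0.75 × (1/34 + 1/66)] = 9.1 points. The largest distortion is 5.5/9.1 = 0.6 standard errors.

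**The case against.** The best reply is that section 14.1.2 never says these patients leave the rate. The population sentence widens the set from the 100 patients of the primary analysis to everyone enrolled, and *developed* can be read cumulatively. A patient graded with contracture at the first follow-up and explanted later would then count. This stands as a limit on size: 16–26% is a ceiling, and the true f may be well below it. It does not help patients lost before any qualifying grade, and no section says what happens to them.

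The causal link is also looser than it first appears. Section 3.0 does not say whether the replacements dominated by contracture include exchange for a new implant, which leaves a gradable breast. No section gives contracture's share of ungradable losses. This stands, and it is why s must be treated as unknown.

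A reader might infer that the rate is biased downward, because contracture drives replacement. The documents do not support that. The sign depends on s against c, neither is given, and at the written cut-off of II or above the assumed range is symmetric about zero.

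Group 2 expander losses before exchange raise a fair question. These patients never had the permanent implant whose contracture is graded, so including them in the denominator is an estimand choice. It also weakens the assumption of equal s behind the between-group figures.

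Finally, section 14.1.2 also says secondary analyses will be done separately by group and names no test, and failure and revision rates are reported as endpoints of their own. A reader would therefore see the losses, but not how many were due to contracture or how they bear on the contracture rate.

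**Conclusion.** The point holds as a mismatch between objective and estimator. As written, section 14.1.2 gives a contracture rate conditional on keeping the prosthesis, and this is more than missing detail because the documents tie some of the losses to contracture. Reading the population rule as excluding these patients is an inference from an undefined term, but it is the natural one and no other text contradicts it.

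The size is bounded and the direction is not established. With nothing assumed about s, the all-patient rate is uncertain over a width of at most f: 16–26 points by the final visit at the section 14.1.1 rates, and less at the first visit or under a cumulative reading. Any between-group distortion is small under the assumptions shown.

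A reader might extend this to the main result. That would be wrong: the primary endpoint counts implant failure itself, among the first 100 patients with sufficient follow-up (section 14.1.1), and this rule does not touch it. The issue should be corrected, but it is confined to a secondary endpoint with no stated power.

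**What to change.** 1. Reconcile the Baker cut-off in section 14.1.2 first. As printed, it labels grades below II as moderate contracture, whereas section 9.3.1 says "Grade I is a normal-appearing, soft breast" and section 3.0 treats grades III and IV as significant contracture. No incidence can be interpreted until this is settled.
2. Define contracture incidence as cumulative by 12/18 and by 24/30 months after IMRT. Count any qualifying grade up to that time, including Group 2's post-IMRT baseline grade. Count removal or replacement performed for contracture as an event, and keep loss for other causes in the denominator as a competing event. State whether Group 2 patients who lose the expander before exchange are in the denominator, and show the rate both ways.
3. Record the cause of each removal or replacement and the last Baker grade before it. The contents of the forms listed in section 16.1 are not shown, so this may already be captured.
4. Report numbers graded and ungraded by reason, and keep the measured-only Baker distribution as a supplementary table labelled as such.

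The cost is analysis-plan wording and at most a short data field. The cause of surgery is best recorded prospectively, since it may be hard to reconstruct later. The reported contracture rate may turn out less favourable.

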7.1.1 Ammonia PET Scans to Correlate IMRT Dose to the Heart

Patients who meet the exclusion criteria listed below (in addition to those listed in section 6.0) will be approached regarding volunteering to receive a $^{13}\text{N-NH}_3$ PET/CT scan during RT simulation, as well as 12-18 months (\pm 6 months) after completion of RT. Ten volunteer patients are expected (n=10, all left-sided), but the study has budgeted enough scans for twelve patients, in the event that a patient is lost to follow-up/expires and cannot have the second scan, or declines the second scan.

Any of the following excludes a patient from the PET/CT subset:

- a. Age >60 years old at time of diagnosis

- b. Diabetes mellitus
- c. Hyperlipidemia
- d. Obesity
- e. Personal history of cardiac illness
- f. Planned IMRT to the right reconstructed breast

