For each patient, if even one out of the two planned studies are unable to generate doses for the heart segments, this patient will be considered as a —failure— towards the endpoint of feasibility. The approach will be declared feasible if we are able to obtain doses for all 17 segments of heart in at least 7 out of 10 patients. Should a patient drop out before they receive their follow-up scan, they will be replaced by another patient, unless the first scan was already a —failure—. We expect n=10 patients, but have budgeted enough scans for 12 patients, in the event a patient gets lost to follow-up/dies and cannot have the second scan, or declines the second scan. However, the decision rule is built by using the first 10 evaluable patients. This decision rule has the following probabilities of declaring success/feasibility.

True feasibility rate	0.85	0.80	0.70	0.60	0.50	0.45
Prob. of declaring feasible	95%	88%	65%	38%	17%	10%

We will further assess feasibility by correlating pre and post-IMRT measures of MBF/CFR with corresponding RT dose delivered to the ventricular myocardium on a global regional and segmental basis. The post-RT studies will help determine the incidence of MBF/CFR changes following radiation as determined by $^{13}\text{N-NH}_3$ PET imaging.

We will measure the correlation between the changes in flow and flow reserve and the dose level in 17 pairs (17 segments per PET data and 17 doses delivered by IMRT). Data will be visually examined first in order to choose the most appropriate correlation coefficient (e.g., Pearson or Spearman or Kendall's Tau, etc., though at this stage we expect that the nonparametric Spearman correlation coefficient will be used). Each patient will thus provide a correlation coefficient. The 10 correlation coefficients for 10 patients in the study will be summarized and descriptive statistics will be computed.

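### PET feasibility rests most on tolerating all imaging sessions, yet a patient with a usable first scan who declines the second because of the procedure is replaced, not counted

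*Combined protocol and SAP*

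**What the plan says.** Section 14.1.3 (PET/CT feasibility endpoint) lists timely delivery of the tracer, successful completion of all scans and, above these, "most importantly, having the patient tolerate all imaging sessions while in the treatment position".

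A patient is a failure "if even one out of the two planned studies are unable to generate doses for the heart segments". The approach is declared feasible if the team can "obtain doses for all 17 segments of heart in at least 7 out of 10 patients".

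On incomplete patients the section says "Should a patient drop out before they receive their follow-up scan, they will be replaced by another patient", with one exception: "unless the first scan was already a" failure. Scans are budgeted for 12 patients to fill 10 places, "in the event a patient gets lost to follow-up/dies and cannot have the second scan, or declines the second scan". Section 7.1.1 gives the same grounds: "cannot have the second scan, or declines the second scan". The decision rule uses the first 10 evaluable patients. Evaluable is not otherwise defined, and no reason for a missed second scan is asked for.

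The section tabulates the chance of declaring feasibility at true rates of 0.85, 0.80, 0.70, 0.60, 0.50 and 0.45 as 95%, 88%, 65%, 38%, 17% and 10%.

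**The concern.** Refusing to repeat a procedure can be a direct sign that it was not tolerated. Each session involves a resting and a stress acquisition of 10-15 minutes each (Section 9.1). Section 11.3 lists dyspnea, headache, dizziness, nausea and chest or abdominal discomfort as temporary effects of the vasodilator. A patient can yield doses for all 17 segments at simulation, find the session unpleasant and decline the next one. She is not a first-scan failure, so the exception does not catch her. The replacement rule treats her like a patient who died or moved away.

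The failure definition and the replacement rule thus pull apart for this one group. She has no second set of segment doses, which the failure sentence would count against feasibility, yet the replacement sentence takes her out of the count. At stake is whether a result of 7 out of 10 can be read as a statement about tolerance. With 10 patients, reclassifying one or two refusals can change the declaration.

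**Working it through.** **Inputs from Section 14.1.3.** 10 evaluable patients; at least 7 successes required; at most 12 patients budgeted; patients who drop out after a successful first scan are replaced; first-scan failures are kept.

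**Assumed input.** q, the share of enrolled patients who have a usable first scan and then decline the second because of the procedure. The documents give no value; 5% and 10% are used.

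**Step 1: the plan's own table.** P(X ≥ 7) for X ~ Binomial(10, p):

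| p | Plan | Recomputed |
|---|---|---|
| 0.85 | 95% | 95.0% |
| 0.80 | 88% | 87.9% |
| 0.70 | 65% | 65.0% |
| 0.60 | 38% | 38.2% |
| 0.50 | 17% | 17.2% |
| 0.45 | 10% | 10.2% |

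Every entry reproduces. The table is right for the success rate among evaluable patients.

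**Step 2: count intolerance-related decliners as failures in the true rate.** Let π be the share of all enrolled patients with doses from both scans, with these decliners as failures. Replacement removes them, so the success rate among counted patients is π / (1 − q), and P(declare feasible) = P(X ≥ 7) for Binomial(10, π / (1 − q)). Unrelated loss is set to zero here.

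- π = 0.50, q = 0.05: 0.50 / 0.95 = 0.526, giving 21.8%.
- π = 0.50, q = 0.10: 0.50 / 0.90 = 0.556, giving 27.8%.
- π = 0.60, q = 0.05: 0.60 / 0.95 = 0.632, giving 46.4%.
- π = 0.60, q = 0.10: 0.60 / 0.90 = 0.667, giving 55.9%.

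The comparison figures without replacement are 17.2% and 38.2%. Stopping at 12 enrolled patients gives about 22% and 26% at π = 0.50, and about 46% and 53% at π = 0.60, for q = 5% and 10% respectively.

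**Step 3: a case with no assumed rate.** Twelve patients start. Two have a usable first scan and refuse the second because of the procedure. Of the other ten, seven succeed and three fail. The rule reads 7/10 and declares feasibility. Over all who started the result is 7/12 = 58%.

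**Step 4: unrelated loss.** First-scan failures are kept while first-scan successes who are later lost are removed, so unrelated loss lowers the counted rate. The inputs below are illustrative.

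- *Unrelated loss only.* First-scan success 0.80, second-scan success 0.75 (true rate 0.80 × 0.75 = 0.60), 10% unrelated loss after a successful first scan. Counted successes: 0.80 × 0.90 × 0.75 = 0.54. Counted patients: 1 − 0.80 × 0.10 = 0.92. Rate: 0.54 / 0.92 = 0.587. P falls from 38.2% to 35.0%.
- *Both.* First-scan success 0.70; 5% of these decline for intolerance (0.70 × 0.05 = 0.035); 10% of the rest are lost for other reasons (0.665 × 0.10 = 0.0665); true rate 0.60. Counted successes: 0.60 × 0.90 = 0.54. Counted patients: 1 − 0.035 − 0.0665 = 0.8985. Rate: 0.54 / 0.8985 = 0.601. P is 38.5% against 38.2%, so there is almost no net change.

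**The case against.** The strongest defence is that the rule is narrower and more open than it first looks. Intolerance that spoils the first scan is a failure and is not replaced. A second scan that is attempted and yields no doses is also a failure. Only patients with a usable first scan who never have the second leave the count. The evaluable denominator is disclosed, and the table is correct for it.

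The link between refusal and intolerance is also uncertain. The stated objective concerns scanning within the simulation session (Section 2.3). The second scan comes 12-18 months (± 6 months) after IMRT, in a voluntary sub-study, and a patient may decline for many unrelated reasons. Replacing deaths and unrelated losses is reasonable. Asking whether each refusal was procedure-related also brings judgement into a rule that is now mechanical.

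All of this stands, and it limits the point. A reader might infer that the table is miscalculated, or that replacement always raises the chance of declaring feasibility. The documents support neither: Step 1 reproduces the table, and Step 4 shows the effect can be cancelled or reversed.

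The defence does not reconcile the replacement rule with the tolerance criterion. Correct counting of first-scan failures does nothing for the refusals that are dropped, and disclosing the denominator does not make it measure tolerance of all sessions.

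**Conclusion.** The point holds in limited form. The plan names tolerance of all sessions as the leading element of feasibility, then removes from the count a patient with a usable first scan who declines the second, whatever her reason. Relative to a rate that counts intolerance-related decliners as failures, the table understates the chance of declaring feasibility: about 22-28% instead of 17% at 0.50, and about 46-56% instead of 38% at 0.60. These ranges rest on an assumed 5-10% of such decliners and no unrelated drop-out. With unrelated loss the net shift may be smaller, nil or reversed, so a net inflation is not established. What needs no assumed rate is that 7 successes among 12 starters, with two intolerance-related refusals, would pass as 7/10. The consequence is minor: one exploratory endpoint in 10 patients, with no effect on the implant-failure analysis.

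**What to change.** Amend Section 14.1.3, and Section 7.1.1 to match:

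- Record the reason for every missed second scan.
- Count a decline as a failure if it is related to the procedure or if no reason is given.
- Replace a patient only for death or for loss unrelated to the scans.
- Define evaluable accordingly, and state that the table applies to that denominator.
- Also report the result over all patients who started, and report success of the simulation-session scan separately.

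The cost is about one sentence on counting, one data field and two extra descriptive summaries. The feasibility result may come out slightly less favourable. Attributing a reason needs some judgement; the analysis over all starters guards against that, since it does not depend on the attribution.
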